11.2 Sample Size Considerations

Sample size calculations assume a 50% reduction in the median duration of diarrhea for the nitazoxanide-treated group compared to those receiving placebo. The median diarrhea duration for the placebo group is assumed to be 135 days, while the median diarrhea duration for the treatment group is assumed to be 67.5 days. Given these assumptions, a sample size of 64 subjects in each arm (128 total) is required to achieve 90% power using the Log-Rank test. Accounting for a 20% attrition rate, final sample size will be 80 in each arm (160 total).

Though discouraged, the protocol allows for subjects in either study group to receive additional nitazoxanide after 28 days. Under the assumptions of treatment efficacy, additional treatment received by placebo subjects would reduce the median duration of symptoms for the placebo group to be closer to that of the nitazoxanide-treated group. It is assumed that subjects who would have the worst study outcomes (longest time to clinical resolution of diarrhea) will be the most likely to receive additional treatment. Subjects receiving additional treatment will be imputed as having the worst outcome (time to resolution censored at 180 days). Accounting for this imputation method, the power attained for the primary comparison was computed via simulation (R version 3.0.3). Estimated power is displayed in the following table, varying the proportion of subjects in each study group who receive additional treatment

		Proportion Receiving Additional Treatment in the Placebo Group						
		0%	5%	10%	15%	20%	25%	30%
Proportion re-treated in the nitazoxanide Group	0%	91.3%	91.6%	91.7%	91.6%	91.8%	92.0%	92.3%
	5%	91.4%	91.5%	91.6%	91.2%	91.2%	91.8%	92.5%
	10%	-	91.5%	92.0%	91.2%	91.8%	91.2%	92.2%
	15%	-	-	90.7%	90.7%	91.0%	91.6%	91.8%
	20%	-	-	-	87.3%	87.1%	87.0%	87.7%
	25%	-	-	-	-	74.0%	73.9%	75.2%
	30%	-	-	-	-	-	40.0%	40.9%

For example, if 15% of placebo subjects receive nitazoxanide, and 5-10% of subjects in the nitazoxanide-treated group receive additional treatment, the power is estimated to be 91.2%. Note that implausible scenarios (where substantially more nitazoxanide subjects receive additional treatment than do placebo subjects) have been omitted from the table.

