11.4.2 Analysis Populations

The safety population (grouped by actual treatment received) will include all subjects who are randomized, have received at least one dose of study treatment and have at least one safety assessment.

The modified intent-to-treat (mITT) population includes all randomized subjects who received at least one dose of assigned study drug. Analyses are performed according to randomized treatment assignment, not the treatment received.

The per-protocol (PP) population will include all subjects who met all inclusion/exclusion criteria, complied with the assigned study product, complied with the daily diary, and were followed up until resolution of symptoms, or completed 180 days without resolution of symptoms.

A subject is considered to be compliant with the assigned study product if he/she takes at least 75% of the scheduled doses through 28 days, and does not receive additional nitazoxanide before their primary outcome is observed.

A subject is considered to be compliant with the daily diary if he/she is missing no more than 1.5/7 days per week over the 8 weeks.

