11.4.3 Efficacy Analyses

11.4.3.1 Analysis of Primary Outcome Measure

The primary efficacy outcome measure is the time from randomization to initial clinical resolution of Norovirus for at least 48 hours, assessed through 180 days, in each study arm. Clinical resolution will be assessed from the daily diary by the subject and will be defined as:

- a. Cessation of vomiting and
- b. No stools classified by the Bristol Stool Chart as diarrhea (Type 6 or 7)

The primary efficacy outcome measure will be assessed in the mITT population. Subjects who receive additional treatment with nitazoxanide other than their assigned study product will be considered censored at 180 days. To assess the effect of the choice of analysis population and additional treatment, the analysis will be repeated as a secondary analysis in the PP population. Sensitivity analyses may be performed to further assess the effect of additional treatment. The details of any sensitivity analyses will be detailed in the Statistical Analysis Plan.

The null hypothesis that the time to first clinical resolution of Norovirus is the same in both treatment arms will be tested using a stratified Log-Rank test to take into account the stratification at randomization. Estimates for median time to resolution and corresponding 95% confidence intervals will be reported for each treatment arm.

We will consider 80% compliance across the monitoring period acceptable [missing no more than 1.5/7 days per week over an 8 week period]. While we will not exclude patients, who are below this compliance for any monitoring period, we will conduct a sensitivity analysis comparing those with few missing values to those with 2 or more missing values per week.

With respect to missing data for the primary endpoint, the primary analysis will be handled as follows:

- Data that are missing after a subject has reached clinical resolution will not affect the primary time to event analysis and therefore will be ignored
- Subjects who drop out, are lost to follow-up, withdraw consent, or otherwise stop completing daily diary entries before clinical resolution will be censored on the day of their last completed diary
- Subjects with a gap in outcome data prior to clinical resolution will be handled depending on their last completed diary entry and their next completed diary entry:

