3.3. Study Definitions and Derived Variables

Diarrhea:

Diarrhea will be defined as Type 6 or 7 on the Bristol Stool chart.

Baseline Value:

The baseline value will be defined as the last value obtained prior to the first dose of study product unless otherwise noted.

Additional Nitazoxanide:

Any nitazoxanide reported as a concomitant medication will be considered additional nitazoxanide.

Initial Clinical Resolution of Norovirus Symptoms:

Clinical resolution of Norovirus symptoms will be assessed from the daily diary by the subject and will be defined as:

- Cessation of vomiting and,
- No stools classified by the Bristol Stool Chart as diarrhea (Type 6 or 7).

Subjects will need to have at least two consecutive daily diary entries where they reported no vomiting, no Bristol Stool Type 6, and no Bristol Stool Type 7 to meet the criteria for initial clinical resolution. There are several variables in the daily diary that indicate whether the subject had diarrhea or vomiting for that day.

Daily Diary Diarrhea Questions:

- Phase 1 (Treatment Phase):
 - Number of Bristol Type 6 stools? (Quantitative)
 - Were there too many Bristol Type 6 stools to count? (Qualitative)
 - Number of Bristol Type 7 stools? (Quantitative)
 - Were there too many Bristol Type 7 stools to count? (Qualitative)
- Phase 2 (Longitudinal Phase):
 - Did you have diarrhea today? (By diarrhea, we mean at least ONE bowel movement that could be described as Type 6 or 7.) (Qualitative)

Daily Diary Vomiting Questions:

- Phase 1 (Treatment Phase):
 - Did you have to take another dose because you threw up the first dose within 1 hour? (Qualitative)
 - How many times did you vomit today? (Quantitative)
- Phase 2 (Longitudinal Phase):
 - Did you vomit today? (Qualitative)

For a day to count towards clinical resolution during the treatment phase, the following responses must be recorded in the daily diary entry:

- Both quantitative diarrhea questions must be 0

- Both qualitative diarrhea questions must be missing (i.e. not “yes”)
- The quantitative vomiting questions must be 0
- The qualitative vomiting question must be “no”

For a day to count towards clinical resolution during the longitudinal phase, the following responses must be recorded in the daily diary entry:

- The qualitative diarrhea question must be “no”
- The quantitative vomiting question must be 0

If a daily diary entry is missing, refer to the imputation rules in Section [6.5](#).

Viral Load:

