5. SAMPLE SIZE CONSIDERATIONS

Sample size calculations assume a 50% reduction in the median duration of diarrhea for the nitazoxanide-treated group compared to those receiving placebo. The median diarrhea duration for the placebo group is assumed to be 135 days, while the median diarrhea duration for the treatment group is assumed to be 67.5 days. Given these assumptions, a sample size of 64 subjects in each arm (128 total) is required to achieve 90% power using the Log-Rank test. Accounting for a 20% attrition rate, final sample size will be 80 in each arm (160 total).

Though discouraged, the protocol allows for subjects in either study group to receive additional nitazoxanide after 28 days. Under the assumptions of treatment efficacy, additional treatment received by placebo subjects would reduce the median duration of symptoms for the placebo group to be closer to that of the nitazoxanide-treated group. It is assumed that subjects who would have the worst study outcomes (longest time to clinical resolution of diarrhea) will be the most likely to receive additional treatment. Subjects receiving additional treatment will be imputed as having the worst outcome (time to resolution censored at 180 days). Accounting for this imputation method, the power attained for the primary comparison was computed via simulation (R version 3.0.3). Estimated power is displayed in [Table 2](#), varying the proportion of subjects in each study group who receive additional treatment.

For example, if 15% of placebo subjects receive nitazoxanide, and 5-10% of subjects in the nitazoxanide-treated group receive additional treatment, the power is estimated to be 91.2%. Note that implausible scenarios (where substantially more nitazoxanide subjects receive additional treatment than do placebo subjects) have been omitted from the table.

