6.4. Covariates and Subgroups

As described in Section 4.4.3, the randomization of treatment assignments and the primary analysis will be performed as stratified by duration of symptoms, transplant type, and age range.

The protocol also defines formal subgroup analyses as exploratory outcome measures; however, the study was not powered to perform these subgroup analyses. Subgroup sensitivity analyses for the primary and secondary outcome measures will evaluate the treatment effect across the following subgroups:

- Additional nitazoxanide: Subjects that took additional nitazoxanide (defined as in Section 3.3) will be excluded from the analyses
- Chromaturia: Subjects with unsolicited self-reported chromaturia (discoloration of urine) will be excluded from the analyses.

[Listing 22](#) and [Listing 11](#) provide listings of subjects that reported chromaturia or took additional nitazoxanide, respectively.

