6.5. Missing Data

All attempts were made to collect all data per protocol. Imputations will only be performed for missing daily diary data as it relates to the primary endpoint. Missing daily diary data for the primary endpoint will be handled as follows:

- Data that are missing after a subject has reached clinical resolution will not affect the primary time to event analysis and therefore will be ignored
- Subjects who drop out, are lost to follow-up, withdraw consent, or otherwise stop completing daily diary entries before clinical resolution will be censored on the day of their last completed diary
- Subjects with a gap in outcome data prior to clinical resolution will be handled depending on their last completed diary entry and their next completed diary entry:
 - If the last completed diary entry and the next completed diary entry have the same outcome (i.e., they are still symptomatic on both days or they have no symptoms on both days), then the gap will be imputed with the same outcome
 - If this imputation results in the subject being defined as having clinical resolution during this gap, their time to resolution will be the median of the interval
 - If the last completed diary entry and the next completed diary entry have different outcomes (i.e., the last one is symptomatic and the next one is asymptomatic, or vice versa), then the gap will be imputed with the symptomatic outcome (no resolution).

[Table 3](#) provides summary statistics (n, mean, median, standard deviation, minimum, and maximum) of the number of imputed diary days per subject given the above imputation rules and the number of overall missing diary days per subject. The above method will be considered the primary imputation method for the primary endpoint. In addition, a sensitivity analysis on the primary endpoint will be conducted using worst case scenario for subjects who drop out, are lost to follow-up, withdraw consent, or otherwise stop completing

daily diary entries before clinical resolution. These subjects will be censored at 180 days (i.e., assuming resolution of symptoms occurred after Day 180). [Listing 9](#) provides subject-level details for the number of diaries missed by week.

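### The Day 180 censoring rule for additional nitazoxanide has no timing condition, so a first resolution observed before re-treatment becomes a non-event, and SAP 8.1 does not say whether the rule applies

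*Protocol*

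**What the plan says.** **The rule.** Protocol 11.4.3.1, on the mITT primary analysis: "Subjects who receive additional treatment with nitazoxanide other than their assigned study product will be considered censored at 180 days". Protocol 11.2 and SAP 5 repeat it in the sample-size text, also without a timing condition. SAP 3.3 makes the trigger broad: "Any nitazoxanide reported as a concomitant medication will be considered additional nitazoxanide".

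**The endpoint.** Time from randomization to initial resolution lasting at least 48 hours, through Day 180. SAP 3.3 operationalises it as at least two consecutive clear diary days.

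**The rationale.** Protocol 11.2 assumes that "subjects who would have the worst study outcomes (longest time to clinical resolution of diarrhea) will be the most likely to receive additional treatment".

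**Neighbouring rules that do carry a timing limit.**
- Per-protocol compliance (protocol 11.4.2; SAP 6.3.2, 9.2 and Table 7) requires that the subject "does not receive additional nitazoxanide before their primary outcome is observed".
- Protocol 11.4.3.1 on missing diaries: "Data that are missing after a subject has reached clinical resolution will not affect the primary time to event analysis".
- The Day 180 worst case in SAP 6.5 and 8.1.1 covers only subjects whose diaries stop before resolution.

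**The SAP's primary analysis.** SAP 8.1 specifies mITT, a Cox model stratified on symptom duration, the definition in 3.3 and the diary rules in 6.5. It does not mention additional nitazoxanide. SAP 6.5 states: "Imputations will only be performed for missing daily diary data as it relates to the primary endpoint". SAP 14.2 does not withdraw the protocol's rule.

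**The concern.** Once a first resolution has been recorded, the endpoint has occurred, and later treatment cannot change its date. A rule triggered by any later nitazoxanide record overwrites that observation with a non-event.

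The documents foresee such a subject. Protocol section 7 and SAP 4.4.7 deal with symptoms that recur after therapy and, directly afterwards, allow nitazoxanide after Day 28 for severe or life-threatening disease.

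Two things are at stake. If the rule is applied literally, real events are lost, and the hazard ratio moves in a direction that depends on the subject's arm. If SAP 8.1 and 6.5 are read as leaving the rule out, the events stay. Two competent analysts could report different primary estimates from the same data, and nothing in the SAP settles which is right before treatment codes are known.

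**Working it through.** **1. Reproduce the plan's figures.** Inputs from protocol 11.2: medians 135 days (placebo) and 67.5 days (nitazoxanide), 64 per arm, two-sided 5%. With exponential times (assumed), P(resolved by Day 180) = 1 − 2^(−180/median):
- placebo: 1 − 2^(−180/135) = 0.603
- nitazoxanide: 1 − 2^(−180/67.5) = 0.843

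Expected events are 64 × 0.603 + 64 × 0.843 ≈ 92.5. Schoenfeld power with hazard ratio 2 is 91.5%.

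The re-treatment table was simulated with a log-rank test and 20,000 runs. The subjects with the longest times in each arm were set to censored at Day 180, with the number rounded up.

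| Re-treated (nitazoxanide / placebo) | Plan | Reproduced |
|---|---|---|
| 0% / 0% | 91.3% | 91.4% |
| 15% / 15% | 90.7% | 91.0% |
| 20% / 20% | 87.1% | 87.2% |
| 25% / 25% | 73.9% | 73.7% |
| 30% / 30% | 40.9% | 39.6% |

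The table is sound for the subjects it models. About 1 − 0.843 = 15.7% of nitazoxanide subjects and 1 − 0.603 = 39.7% of placebo subjects are unresolved at Day 180 anyway. Recoding the longest times therefore changes little until the nitazoxanide share passes about 15%. The table does not model early resolvers who relapse.

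**2. Follow one subject through the rules.** Suppose first resolution on Day 20, relapse on Day 40, and nitazoxanide on Day 45 (days invented).
- Endpoint definition: event on Day 20.
- Protocol 11.4.3.1, literally: censored at Day 180.
- Per-protocol set: not excluded for the nitazoxanide, because the outcome came first. SAP 8.1.1 repeats the primary analysis there, so under the literal rule this subject is kept and counted as unresolved.
- SAP 8.1 with 6.5: event on Day 20, if 6.5 is taken as the complete list of changes to the data.
- SAP 6.4 sensitivity analysis: removed. The event is not restored.

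**3. Size for the 31 enrolled.** The documents give no arm or stratum split, so five were assumed (placebo, nitazoxanide per stratum): (5,5)+(10,11); (8,8)+(7,8); (11,11)+(4,5); (7,9)+(6,9); (9,7)+(9,6). Exponential times at the planned medians; stratified Cox model; about 6,000 runs each. One resolver with an event before Day 120 is recoded as censored at Day 180. Median within-run change in the hazard ratio:
- nitazoxanide subject recoded: × 0.838, 0.841, 0.836, 0.857, 0.808
- placebo subject recoded: × 1.217, 1.216, 1.215, 1.254, 1.177

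For (8,8)+(7,8) the median hazard ratio moves from 2.02 to 1.68, or from 2.01 to 2.42. With both medians at 135 days the factors are 0.800 to 0.854 and 1.172 to 1.247.

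Hand check using rate = events / person-days:
- Nitazoxanide, 16 subjects: 16 × 0.8425 = 13.48 events over 1,312.7 person-days. Mean event time before Day 120 is 48.0 days, so recoding one adds 180 − 48.0 = 132.0 days. Rate ratio = (12.48 / 1,444.7) / (13.48 / 1,312.7) = 0.841.
- Placebo, 15 subjects: 9.05 events over 1,762.1 person-days, mean event time 53.9. Rate ratio = (8.05 / 1,888.2) / (9.05 / 1,762.1) = 0.830, so the hazard ratio is multiplied by 1 / 0.830 = 1.20.

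**4. Against the precision available.** With 15 placebo and 16 nitazoxanide subjects, SE(log HR) ≈ √(1/9.05 + 1/13.48) = 0.43. The 95% CI around 2.0 is exp(0.693 ± 1.96 × 0.43) ≈ 0.86 to 4.65. The shifts in step 3 are |ln 0.86| / 0.43 = 0.35 to |ln 1.25| / 0.43 = 0.52 standard errors.

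**5. Planned design, for scale.** Recoding 6 resolvers in each arm of 64 (assumed) removes 12 of about 92.5 events and leaves the median hazard ratio at 1.97. Unequal counts move it: 6 placebo and 3 nitazoxanide give 2.23; 3 and 6 give 1.75.

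**The case against.** **It could be a deliberate failure strategy.** Counting someone who was clear for 48 hours and then needed urgent rescue as a failure is a legitimate composite strategy. The documents do not state that strategy, though. Their reason concerns subjects with the longest times, and the per-protocol wording treats an earlier resolution as already observed. Together these suggest a rule meant for unresolved subjects that lacks its limiting clause.

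**The route is narrow and the effect small.** Nitazoxanide after Day 28 needs the local investigator's attestation of urgency. No affected subject is shown. SAP 14.2 calls the updated analyses mainly descriptive, and the shift is about half a standard error or less. All of this stands, and it limits the weight of the point. A hazard ratio, confidence interval and p-value are still planned.

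**The SAP may already inherit the rule.** Its preface says it expands on the protocol, SAP 5 restates the rule, and 6.5 sits under missing data. That reading is fair. It would settle that the rule applies, but then the rule applies with no timing limit.

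**A stronger reading to avoid.** A reader might infer that the rule inflates type I error. Simulations that force more recoded resolvers into one arm do reject too often, but the imbalance is imposed. If the drug affects neither resolution nor relapse nor re-treatment, the blinded arms are exchangeable and the test keeps its size. With 64 per arm, both medians 135 days, and each resolver before Day 120 recoded with the same probability in both arms (0%, 10%, 20% or 30%), rejection was 4.9% to 5.4% over two sets of 20,000 runs per setting. Inflation requires re-treatment after resolution to differ between arms, and the documents give no evidence on that.

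**Conclusion.** The point holds as a defect in a stated rule. As written, the rule turns an observed first resolution into a non-event for anyone re-treated later. That is inconsistent with the endpoint, with the 11.2 rationale and with the per-protocol definition. SAP 8.1 leaves its use open, and SAP 5 and 6.5 point in different directions.

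The practical size is modest and uncertain. The number of affected subjects may be zero. If there is one, the hazard ratio changes by a factor of about 0.81 to 0.86 (nitazoxanide) or 1.18 to 1.25 (placebo), well within its confidence interval. These factors rest on exponential times, the planned medians, the assumed splits and a resolver with an event before Day 120. The direction cannot be predicted. Neither a fixed power loss nor a general type I error inflation is claimed. The clarification should be made because it is cheap and settles the primary coding in advance.

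**What to change.** In SAP 8.1, before unblinding, state that Day 180 censoring for additional nitazoxanide applies only when that nitazoxanide was started before first clinical resolution. State also that a resolution observed earlier is kept as an event on its own date, in both the mITT and PP analyses. Make the same change in protocol 11.4.3.1 only if the protocol is amended for other reasons, since enrolment had already stopped when the SAP was written.

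The cost is one sentence and no new data. Listing 11 already plans the days post randomization for additional nitazoxanide from the concomitant medication form, and the diaries give the date of first resolution.

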11.4.3.2 Analysis of Secondary Efficacy Outcome Measures

All secondary efficacy outcome measures will be assessed in the mITT and PP populations separately.

The secondary efficacy outcome measures are as follows:

1. The time from the randomization to first negative viral load through 180 days.
2. The change in viral titer between Day 1 and Day 180.

Secondary outcome measure 1 will be assessed through Kaplan-Meier curves along with results from a Log-Rank test to compare the time from randomization to first negative viral load between the nitazoxanide treated group and the placebo group.

Secondary outcome measure 2 will be assessed using analysis of covariance (ANCOVA) adjusting for baseline viral titer.

11.4.3.3 Sensitivity Analysis of Primary and Secondary Efficacy Outcome Measures

As a sensitivity analysis, all primary and secondary efficacy analyses will be conducted among the subgroup of subjects who do not report chromaturia (discoloration of urine) based on unsolicited self-reporting, in order to help determine if knowledge of this side effect may have impacted these outcomes.

